## CHANGE LOG

VERSION NUMBER	ISSUED BY (INITIALS)	COMMENTS (MAJOR CHANGES SINCE LAST REVISION)
1.0	██████	Document established in template version 5.0
2.0	██████	p12: Label added
3.0	██████	Minor editorial changes p12: Label changed to label specifying "Single use" p18: Subjects are requested to meet with full bladder at visit 1 added p21: Concomitant disease deleted p24+25: remuneration with raised from DKK1000 to DKK 1200 p26: Confidentiality Agreement changed to Secrecy Agreement p26 consent to pass on social security number (CPR-number) to the Danish tax authorities, added
4.0	██████	p22: As this study only consist of one study visit, expected drop-outs are 0. Should there be a drop-out, will these be replaced until 12 patients has finalised visit 1. p26: Deleted: This procedure also applies to informed consent obtained from a subject's legal representative. The procedure cannot waive the subjects' legal rights.
5.0	██████	p7+p15: Primary endpoint: "Sensor capability to generate a readable sensor profile" added. Exploratory Secondary endpoints deleted p12: Label with expiry date pictogram added  p15 6.1.3: "Due to the early concept supporting purpose of this trial, no primary endpoint is defined" deleted.  p18: Termination section added.  P19: Tabel 1 "Written informed consent" changed to "Signed informed consent". Signed Letter of authority, "Investigator" replaced by "Subject"  "...and endpoints – during catheterization" deleted  "Urine pressure prior to and during voiding (sensor)" Changed to "Sensor data prior to and during voiding"  p20" Written informed consent, in- and exclusion criteria and all Adverse events occurring in the investigation will be 100% verified for timely completion for all subjects enrolled in the investigation". Changed to "Signed informed consent, signed Letter of authority, in- and exclusion criteria and all Adverse events occurring in the investigation will be 100% monitored for all subjects enrolled in the investigation."  p22: "Readable sensor profiles versus non-readable sensor profiles will be summarized" added. "Analysis of explorative secondary endpoints" changed to "Analysis of primary endpoint".  p23: Clinical Investigation Plan deviations, section 10 updated.
6.0	██████	The overall timeline for the study has been changed from December 2018- March 2019, till March 2019- August 2019.

## > SYNOPSIS OF THE CLINICAL INVESTIGATION

---

### Background

Intermittent catheterisation is the preferred method of bladder emptying for persons with chronic urine retention due to neurogenic bladder dysfunction following e.g. spinal cord injury, or due to an enlarged prostate, etc. Coloplast A/S manufactures different catheters and devices for incontinence and works continuously to improve them.

The purpose of this study is to test the pressure sensor capabilities in a clinical environment. The sensor has shown good readable results in pre-clinical tests. Given the complex pressure conditions in the human body with pressure contributions from e.g. body movement, bowel peristalsis, heartbeat etc, the next step is to test the sensor capability to generate readable pressure measurement before and during catheterisation in healthy volunteers and to evaluate the extent of artifacts on the sensor readings.

### Objective

To explore data obtained from a sensor connected to an intermittent catheter prior to and during voiding.

### Primary endpoint and secondary endpoint(s)

#### Primary endpoint

Sensor capability to generate a readable sensor profile

#### Secondary endpoints

Adverse events

### Pass/fail criteria

No formal success criteria are applied in this exploratory study. However, it is expected that the study will provide useful data to guide efforts in development of the pressure sensor.

### Design of the investigation

Single arm - open-label study.

Each participating subject will be asked to conduct:

- Information visit
- Visit 0 – inclusion visit
- Visit 1 – Test visit

### Population

The population consists of 12 healthy volunteers. Both male and female are eligible for enrolment. Minimum 4 subjects of each gender must be enrolled and subjects must comply with the following inclusion and exclusion criteria:

Inclusion criteria:	Exclusion criteria:

 
1. Have given written informed consent
 
2. Be at least 18 years of age and have full legal capacity
 
3. Negative pregnancy test for fertile women
 
	
 
1. Previous history of significant genitourinary disease including congenital abnormalities and surgical procedures performed in the urinary tract
 
2. Symptoms of urinary tract infections (frequent urination, stinging and pain at urination)
 
3. Participation in any other clinical investigations during this investigation (Inclusion → termination)
 
4. Known hypersensitivity toward any of the test products
 
5. Are pregnant (positive pregnancy test) or breast feeding.
 

### Test products

The tested medical device is a pressure sensor connected to an intermittent CE-marked commercially available catheter. The sensor is built around a tubular part that will be connected at the end of the catheter connector: urine will flow through the catheter directly into sensor lumen and out into toilet.

### Investigation approval

The investigation will be approved by the Ethical Committee in Denmark and the Danish Medicines Agency before investigation initiation.

## > LIST OF ABBREVIATIONS

ABBREVIATION	WRITTEN OUT	EXPLANATION
AE	Adverse Event	See section 14
CA	Competent Authority. In this CIP the Danish Medicines Agency.	
CIP	Clinical Investigation Plan	
CM	Clinical Manager	Coloplast A/S study operational responsible and author of this Evaluation
CRF	Case Report Form	
DQF	Data Query Forms	A DQF is a query specifically used in clinical research. The DQF is the primary data query tool from the sponsor to clarify discrepancies and ask the investigator for clarification. The DQF is part of the data validation process in a clinical investigation.
EC	Ethics Committee	
LSO	Last Subject Out	
PI	Principal Investigator	Qualified person responsible for conducting the clinical investigation at an investigation site. If the clinical investigation is conducted by a team of individuals at an investigation site, the PI is the responsible leader of the team. Whether this is the responsibility of an individual or an institution can depend on national regulations.
SAE	Serious Adverse Event	

> **SIGNATURE PAGE**

---

All sponsor representatives declare by their signature on the electronic signature page that they will follow this Clinical Investigation Plan CP304 in accordance with the Declaration of Helsinki, ISO 14155 and the Medical Device Directive/Regulation.

---

### 1.3. Other

All delegated tasks from Investigator to Study Nurses will be documented in the Site Personnel Signature and Delegation List.

#### 2.1.1. Identification, traceability and labelling of device

#### 2.1.2. Clinical investigation purpose of device

The purpose of the investigational device in the proposed clinical investigation is to capture pressure data prior to and during voiding using a CE-marked commercially available catheter.

#### 2.1.3. Intended population for the device

People who are depending on intermittent catheterization will be eligible to use the final device when and if commercially available.

#### 2.1.4. Description of investigational device

The medical device subject to test, is a sensor connected to an intermittent CE-marked commercially available catheter, as shown on the figure below. Catheters to be used will be SpeediCath® Standard male/female, Nelaton tip. The investigational device will not be in direct contact with subjects.

Figure 1 Test device connected to catheter and data capture

### 2.1.5. Handling and training

Site staff will receive proper training in the use of the device prior to study start.

## 3. Justification for the conduct of the clinical investigation

Intermittent catheterisation is the preferred method of bladder emptying for persons with chronic urine retention due to neurogenic bladder dysfunction following e.g. spinal cord injury, or due to an enlarged prostate, etc. Coloplast A/S manufactures different catheters and devices for incontinence and works continuously to improve them.

The purpose of this study is to test the pressure sensor capabilities in a clinical environment. The sensor has shown good readable results in pre-clinical tests. Given the complex pressure conditions in the human body with pressure contributions from e.g. body movement, bowel peristalsis, heartbeat etc, the next step is to test the sensor capability to generate readable pressure measurement before and during catheterisation in healthy volunteers and to evaluate the extent of artifacts on the sensor readings.

[Redacted text block]

## 4. Ethical Considerations, risks and benefits

The evaluation is conducted in accordance with current law and applicable standards see section 12.

The rights, safety and well-being of human subjects will prevail over interest of science and society.

Subjects participating in the evaluation will be catheterized using a CE-marked commercially available catheter with the test device connected. The catheterization will be performed by urology nurses from Rigshospitalet Department of Urology with many years of experience in conducting intermittent catheterization.

There are no direct benefits for the participating subjects involved, but, by participating in this investigation, the subjects will contribute with important information for developing improved solutions for urinary intermittent catheterisation, that in turn may benefit individuals who are dependent on catheters for emptying their bladder.

The evaluation is conducted in accordance with 'The Declaration of Helsinki', 1964, last amended at the 64th WMA General Assembly, Fortaleza, October 2013, and ISO 14155 and the Medical Device Directive/Regulation.

## 5. Objectives and hypotheses of the clinical investigation

### 5.1. Objective

The objective is to explore data obtained from a sensor connected to an intermittent catheter prior to and during voiding.

### 5.2. Risks and anticipated adverse device effects to be assessed

Risks associated with the investigation may be discomfort or stinging in the urethra during the catheterisation. Furthermore, there may be a risk of micro-trauma and haematuria after catheterisation, which is expected to heal within 1-3 days. The trial setting is not expected to result in increased frequency or severity of the known risks associated with urethral catheterisation

## 6. Design of the clinical investigation

### 6.1. General

This clinical investigation is based on an open explorative design evaluating the sensor ability to record readable data in healthy volunteers and the extend of artifacts influencing data quality and readability in healthy volunteers.

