### **6.1.1. Primary endpoint**

#### **Primary endpoint**

Sensor capability to generate a readable sensor profile.

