### **6.1.3. Rationale for selection of measurements and endpoints**

The endpoints have been chosen to explore pressure sensor capability to generate readable pressure data in a catheter in a clinical environment.

Data recordings will be considered versus what is known for urine parameters from physiology, clinical practice and will be considered versus background data obtained via a standard uroflowmeter during voiding.

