### **6.4.3. Foreseeable factors that may compromise the outcome / results**

No foreseeable factors are expected to compromise the outcome/results of the design.

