#### **Analysis of primary endpoint**

Sensor data will be graphically presented over time and sensor capability to generate a readable sensor profile will be visually evaluated (FAS) and considered versus what is known on bladder physiology.

In case of an unexpected profile, the sensor profile will be considered in relation to the data on urine flow and voided volume, obtained via a standard uroflow meter.

Readable sensor profiles versus non-readable sensor profiles will be summarized.

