## **7.2. Sample size**

Due to the conceptual nature of this trial no formal sample size calculation has been performed. It is assumed that 12 healthy volunteers will be adequate for evaluating the data quality of the sensor.

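### Does the plan leave the extent of artifacts, one of its stated purposes, without a result?

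*Combined protocol and SAP*

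**What the plan says.** The synopsis background, repeated word for word in section 3, gives two reasons for moving from pre-clinical tests to volunteers. One is to see whether the sensor yields readable pressure measurements. The other is "to evaluate the extent of artifacts on the sensor readings". Section 6.1 restates both aims, the second as "the extend of artifacts influencing data quality and readability in healthy volunteers". The formal objective in section 5.1 does not mention artifacts; it is to "explore data obtained from a sensor connected to an intermittent catheter prior to and during voiding".

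The primary endpoint is "Sensor capability to generate a readable sensor profile", and the secondary endpoint is adverse events. Under the primary analysis in section 7.1, sensor data are plotted over time and readability is judged visually, after which "Readable sensor profiles versus non-readable sensor profiles will be summarized". Section 7.1 also states that exploratory qualitative analysis will be done in graphics software.

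Section 6.5.1 requires pressure and flow to be plotted for each catheterisation and the data quality evaluated visually. Section 6.1.3 says recordings will be considered against "background data obtained via a standard uroflowmeter during voiding". On numbers, section 7.2 says "It is assumed that 12 healthy volunteers will be adequate for evaluating the data quality of the sensor". Section 16 requires the report to evaluate critically all data collected.

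**The concern.** Body movement, bowel activity and heartbeat are the reason the protocol gives for testing the sensor in people at all. A reader therefore expects an endpoint or table that says how much they disturbed the traces. There is none. A readable/non-readable count cannot supply it, because a trace may be disturbed for part of its length and still be readable.

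The objective also names two periods, before and during voiding, but the flow-chart in section 6.4.4 collects both in one row and section 7.1 summarises whole profiles. The uroflow variables describe voiding only. Section 6.4.3 adds to the unease: "No foreseeable factors are expected to compromise the outcome/results of the design".

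If the plan gave no other route to this information, the study could end with a count of readable traces and nothing on what disturbs them or when. That would be a loss for sensor development, which is the use the synopsis foresees.

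**Working it through.** The documents give no artifact rate, readability rate or power figure, so there is no stated number to reproduce. The check is mainly a comparison of sections.

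**1. How often artifacts are named as a purpose.** The synopsis background and section 3 are the same paragraph, and section 6.1 is a separate statement. That makes two distinct statements. The objective in section 5.1 is not one of them.

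**2. What must be produced for each recording.**

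| Section | Required step | Can it show artifacts? |
|---|---|---|
| 6.5.1 | Pressure and flow plotted over time; data quality judged visually | Yes, for each catheterisation |
| 7.1, primary analysis | Sensor trace plotted; readability judged visually and set against bladder physiology | Yes |
| 7.1, opening | Exploratory qualitative analysis with graphics | Yes |
| 7.1, primary analysis | Readable/non-readable summary | No, count only |
| 16 | Critical evaluation of all collected data in the report | Yes |

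The plotting, the quality reading and the qualitative analysis are commitments, not options. Section 6.1 describes the artifacts of interest as those that affect data quality and readability, and these are the two properties judged on each trace.

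**3. What the count hides.** Suppose *readable* tolerates some disturbance; the plan does not define the term. Each readable recording then falls into one of 2 × 2 = 4 states (each period clear or disturbed), and the count reports all four as one. Twelve clean traces and twelve partly disturbed but readable traces both give 12/12. This is true of the count alone: the plots and the quality readings would differ between the two cases.

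**4. The merged periods, with assumed rates.** Let 95% of pre-voiding and 70% of voiding traces be readable.
- If a profile counts as readable only when both periods are, the rate lies between 0.95 + 0.70 − 1 = 65% and min(0.95, 0.70) = 70%. Under independence it is 0.95 × 0.70 = 66.5%.
- If either period suffices, it lies between max(0.95, 0.70) = 95% and 100%.

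The count would not show which period failed. The plot of each of the 12 traces would, since sensor data are recorded in both periods and drawn against time.

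**5. What a formal artifact table could establish.** With n = 12 the exact (Clopper-Pearson) 95% intervals are 73.5% to 100% for 12/12, 21.1% to 78.9% for 6/12, and 0% to 26.5% for 0/12. The chance of seeing an artifact type at least once is 1 − (1 − p)^12: 46% at p = 5%, 72% at p = 10%, 93% at p = 20%. Twelve traces support description but no precise rate, so tabulation would add little to a described set of plots.

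**6. Uroflow and foreseeable factors.** Section 6.1.3 sets recordings against uroflow data without condition, and section 6.5.1 plots flow for every catheterisation; the restriction in section 7.1 to unexpected profiles does not remove either. A flowmeter has nothing to measure before flow starts, so the missing pre-voiding reference is a property of the instrument. Section 6.4.3 concerns factors that would compromise the results. Artifacts are what the study sets out to observe, so meeting them does not contradict that section.

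**The case for a change.** The best case for a change is that none of these provisions obliges anyone to report artifacts. Section 6.5.1 belongs to the monitoring plan and its output is filed, the qualitative analysis in section 7.1 has no stated content, and section 16 is general. A sponsor could satisfy all of them and say little about extent. A listing of 12 recordings × 2 periods = 24 rows needs no extra subject or visit, and insertion times and movements are more reliable if noted at the test visit than if reconstructed later.

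Part of this stands: section 7.1 names no artifact output and does not divide the readability summary by period. The rest is weaker. A report that appraises all the data critically and shows 12 plotted traces can hardly pass over visible disturbances when they are a declared purpose. Scoring the share of time disturbed would give apparent precision to a subjective reading, and heartbeat and bowel activity would mostly remain unattributable. Noting event times adds a task during catheterisation. Whether timing is already captured cannot be judged, because the case report form and the figure of the data capture set-up are not in the documents.

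**Conclusion.** No change is needed. The plan omits a reporting detail that the analysts can supply from readings they must make anyway, by describing the artifacts seen on each trace before and during voiding. The omission touches no primary result, error rate, sample size or decision rule, because the study is exploratory, has no pass/fail criterion and made no formal sample size calculation. A new artifact endpoint or assessment method would be a significant change under section 9, to be notified to or approved by the ethics committee and the authority, for a descriptive gain that 12 traces already offer.

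This rests on two assumptions: that the visual evaluation is done for all 12 recordings as written, and that the plots cover both periods, as the data collection in section 6.4.4 implies. The percentages in the working are illustrations with assumed rates and say nothing about the sensor's actual performance.

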#### Overall:

- Single arm. Open-labelled, not randomized
- Healthy volunteers

#### Duration:

#### Information visit:

Oral and written information about the evaluation is given by the PI or his/her representative. Subjects can continue to visit 0, inclusion visit, the same day - if the subject has decided on participation and practical possible.

#### Visit 0 – Inclusion visit:

Informed consent signed.

Subjects can continue to visit 1 - test visit the same day - if practical possible.

#### Visit 1 – test visit:

1h test visit at Rigshospitalet. Fertile females will be asked to perform a pregnancy test. Subject is asked about symptoms for urinary tract infections (frequent urination, stinging or pain at urination). If negative for these symptoms, the subject will be catheterised with (SpeediCath® Standard, male/female, Nelaton tip depending of the gender) with fitted pressure sensor. The urine is led into a standard urine flowmeter.

### **6.1.1. Primary endpoint**

#### **Primary endpoint**

Sensor capability to generate a readable sensor profile.

### **6.1.2. Secondary end points and exploratory endpoints**

#### **Secondary endpoints**

- Adverse events

### **6.1.3. Rationale for selection of measurements and endpoints**

The endpoints have been chosen to explore pressure sensor capability to generate readable pressure data in a catheter in a clinical environment.

Data recordings will be considered versus what is known for urine parameters from physiology, clinical practice and will be considered versus background data obtained via a standard uroflowmeter during voiding.

### **6.1.4. Discussion of clinical investigation design**

This is a single arm, open-labelled, not randomized investigation. The population consists of 12 healthy volunteers. Both male and female are eligible for enrolment. Minimum 4 subjects of each gender must be enrolled for one test visit. The reason for this design is the exploratory nature of the investigation.

## **6.2. Investigational device and comparator(s)**

The evaluation does not include comparator devices.

## **6.3. Subjects**

To be included in the investigation, the subjects must comply with the selection criteria described in section 6.3.1 .

### **6.3.1. Inclusion criteria for subject selection**

Subjects participating in the clinical investigation must comply with the following criteria:

**Inclusion criteria:**

1. Have given written informed consent
2. Be at least 18 years of age and have full legal capacity
3. Negative pregnancy test for fertile women

Inclusion 3: Women are considered fertile if they have had a least one period during the last 12 months

**6.3.2. Exclusion criteria for subject selection**

Subjects complying with the following criteria must be excluded from participation in the clinical investigation:

**Exclusion criteria:**

1. Previous history of significant genitourinary disease including congenital abnormalities and surgical procedures performed in the urinary tract
2. Symptoms of urinary tract infections (frequent urination, stinging and pain at urination)
3. Participation in any other clinical investigations during this investigation (Inclusion → termination)
4. Known hypersensitivity toward any of the test products
5. Are pregnant (positive pregnancy test) or breast feeding.

